The 7-day cut off derives from the data in the literature with respect to the average times of onset of the lesions (4th day in the medical field, 5° in the surgical field and 3° in the intensive care unit) with standard deviations that allow to affirm that after 7 days in the acute patients the PD event is extremely rare (Palese 2017; Chiari 2017; Santamaria 2015). PD is defined as a damage to the skin and underlying tissues due to pressure, stretching or friction or a combination of these factors (NPUAP 2014). The incidence of PD is represented by the PD who develop during hospitalization and are not present when the patient is admitted. The injuries will be classified according to the classification defined by the guideline prepared by NPUAP 2014. (attachment).

Secondary Endpoints:

- Incidence of PD to the sacrum category ≥ II ° according to the NPUAP scale
- Skin irritation / damage due to adhesive dressing
- Day of onset of the PD
- Number of dressings used
- Number of patients who stop treatment due to discomfort caused by the dressing (withdrawal)

Other study variables / data collected

- Gender
- Age

- Origin of the patient: first aid, another ward or facility, Short Observation (OBI), Home
- Pregressed (healed) PD to the sacred
- Patient risk level measured with the Braden scale (Pancorbo-Hidalgo PL 2006)
- Days in the study
- Use of the diaper
- Use of the bladder catheter
- Use of anti-decubitus surface (static, preventive dynamics, curative dynamics and air release)
- Daily presence of the caregiver (presence at least during a meal, never, always)

Study Population

Inclusion Criteria:

- Patients at risk of developing PD measured with the Braden scale (Braden \leq 16) with intact sacral skin and / or with signs of healing from previous sacral lesions.
- Patients or legal guardians who consent to the study
- Adult patients
- . Male and female gender
- Expected hospital stay and / or life expectancy > 72 hours
- Patients hospitalized for no more than 24 hours

Exclusion criteria:

- Patients with known allergy to the products under study or with dermatological pathologies that prevent the use of topical products
- Patient with, upon entering the ward, advanced preventive dressing in the sacral region

Design

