- At discharge or on the appearance of pressure lesion on the sacrum ≥ 2nd category, the CRF is closed and the patient ends the study. If the patient has developed PD the treatment of the lesion will be performed according to the hospital policy.
- The medication will be removed, however, no later than the first 7 days of admission after which the patient ends the study.

Study exit criteria

- Withdrawal of informed consent before randomization
- Not randomized within 24 hours of admission

Conclusion of the study in the single recruited subject

- Withdrawal of consent after randomization
- The appearance of irritation to the skin caused by the dressing. The dressing is removed, reported in CRF and irritation treated as per hospital policy.
- At the request of the patient due to discomfort due to preventive medication.
- On discharge / death / transfer to ward not involved in the study before the 7th day after randomization
- After 7 days from randomization in the absence of PD to the sacrum
- The appearance of pressure injury to the sacrum higher than the first category

Sample size

From a randomized monocentric study of at-risk patients with a hip fracture where polyurethane foams were used in prevention, the incidence in the experimental group was 4.5% while in the control group of 15.4%. Similar deltas had also been identified in other trials in intensive care patients. Assuming similar results in the population subject of the present study and taking into account an alpha error of 0.05 and a beta error of 20%, it is necessary to enroll at least 228 patients at risk. In order to allow analyzes by subgroup (see the "statistical analysis" section) the sample size must be guaranteed for each area (medical, surgical, intensive).

Taking into account also a possible loss at the follow-up of 10% and also assuming a 10% withdrawal rate, the necessary sample will be 280 patients per area and therefore a total of 840 patients (420 per arm). Each hospital involved will enroll 40 patients per area involved in that specific hospital.

Randomization

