At the Research Center for Health Professions of the Rizzoli Orthopedic Institute in Bologna (coordinating center), using the site: www.randomization.com, a randomization list will be generated in blocks of 10. A sequence of opaque envelopes will be prepared with outside a progressive number. Inside the envelope a label will be placed that will contain the words "yes" or "no", according to the sequence indicated by the generated list.

The envelopes will always be sealed at the Research Center and the list kept under lock and key. The envelopes will be placed in a dedicated box and delivered to the nursing research manager of the hospitals involved in the study. In each ward/area a reference nurse will be identified and 40 envelopes delivered.

Statistical analysis

The analysis of the results will be carried out for Intention to Treat.

All continuous data will be expressed in terms of average and standard deviation. One Way ANOVA will be used to evaluate the differences between the averages of the experimental and comparison group. If the Levene test for homogeneity of variance were significant (p <0.05), the Mann Whitney test will be used. For all dichotomous variables the incidence, relative risk, relative risk reduction and number needed to treat will be calculated. The exact

Fisher test will be used to evaluate the differences between the incidences of different outcomes between the experimental group and the control group.

Subgroup analysis:

- by area of belonging (medical, surgical or intensive)
- by risk level according to the Braden classification: Severe (total score 9); High Risk (10-12) Moderate Risk (13-14); low Risk (15-16). (Pancorbo-Hidalgo PL 2006)
- by origin (domicile vs. other settings)

For all tests, a p <0.05 will be considered significant.

The statistical analysis will be done using the "Statistical Package for the Social Sciences" (SPSS) software version 15.0 (SPSS Inc., Chicago, USA)

Possible deviations from the protocol and / or critical issues and related behavior to be followed in all situations

- If the dedicated nurse, during the daily inspection, realizes that the sacral MSP (in the patients of the experimental arm) has been removed without being positioned anymore, he provides to reposition it, marking in the CRF that the patient for that day remained without.

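### Switching from ANOVA to Mann-Whitney on a significant Levene test does not correct for unequal variances, and loses the 5% level when unequal spread combines with unequal group size or skew

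*Combined protocol and SAP*

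**What the plan says.** The Statistical analysis section gives one rule for all continuous variables. The summary is fixed: "All continuous data will be expressed in terms of average and standard deviation". So is the target: "One Way ANOVA will be used to evaluate the differences between the averages of the experimental and comparison group". There is one exception: "If the Levene test for homogeneity of variance were significant (p <0.05), the Mann Whitney test will be used". The level is common to every test: "For all tests, a p <0.05 will be considered significant".

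A significant Levene test is the only route away from ANOVA. No unequal-variance test is planned, and nothing asks about the shape of the distribution.

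The Secondary Endpoints list includes "Day of onset of the PD". The continuous rule is the only planned analysis that fits it. The primary endpoint and the category II or higher endpoint are incidences, assigned to Fisher's exact test.

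**The concern.** The rule detects unequal variance and responds with a test that is not built for it. With two arms, ANOVA is the pooled-variance t test of a difference in means. Mann-Whitney asks whether values in one group tend to exceed those in the other, and its reference distribution assumes identical distributions under the null. When spreads differ it tests something other than the averages, and its rejection rate under equal means need not be 5%.

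The data therefore choose the hypothesis. A reader could be shown two means and SDs beside a p value that does not refer to them.

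Day of onset is where this matters most. It exists only for patients who develop an ulcer, and if the dressing works as planned those groups will differ greatly in size. At stake is a false or a missed claim that the dressing changes when ulcers appear.

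**Working it through.** **Inputs from the Sample size section.** The planning rates are 4.5% and 15.4% ("the incidence in the experimental group was 4.5% while in the control group of 15.4"%), with alpha 0.05 and power 80%. The base number is stated as "it is necessary to enroll at least 228 patients at risk". The inflated total is 840, or 420 per arm.

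**Reproducing the plan's figure.** Two proportions, unpooled variance, two-sided:

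n per arm = (1.960 + 0.842)² × (0.154×0.846 + 0.045×0.955) / (0.154 − 0.045)² = 7.849 × 0.1733 / 0.01188 ≈ 114.5

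The total is 228.9, which agrees with 228 to within rounding. Inflation gives 228/(0.9×0.9) ≈ 282 or 228/0.8 = 285, close to the stated 280 per area; 3 × 280 = 840.

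**Group sizes for day of onset.** 420 × 0.045 = 18.9 and 420 × 0.154 = 64.7, so about 19 versus 65 if all 840 patients are analysed and the planning rates hold.

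**Assumptions.** The documents give no SD or distribution for any continuous variable, so both are assumed and varied. Levene's test is taken as mean-centred and all tests as two-sided, since neither is stated. True means are equal throughout.

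**Method.** Simulate both groups and apply Levene at 0.05. Use Mann-Whitney if it is significant, otherwise ANOVA, and count p < 0.05. Normal data and the SD 2 vs 1 day setting used 20,000 runs (simulation standard error near 5%: √(0.05×0.95/20,000) ≈ 0.15 points). The skewed (gamma) rows used 4,000 to 6,000.

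| Setting | Protocol's rule | Welch |
|---|---|---|
| 19 vs 65, equal SD, normal | 5.0% | 5.2% |
| 420 vs 420, normal, SD ratio 1.5 / 2 / 3 | 5.5 / 5.9 / 7.0% | 5.3 / 5.1 / 5.0% |
| 19 vs 65, normal, smaller group wider, ratio 1.5 / 2 / 3 | 8.9 / 10.3 / 13.0% | 5.2 / 5.0 / 4.9% |
| 19 vs 65, normal, larger group wider, ratio 1.5 / 2 / 3 | 2.1 / 1.7 / 1.2% | 4.9 / 4.7 / 5.0% |
| 19 vs 65, days 1–7, SD 2 vs 1, smaller group wider | 12.2% | 5.1% |
| 19 vs 65, days 1–7, SD 2 vs 1, larger group wider | 1.4% | 5.1% |
| 19 vs 65, skewed, ratio 2, smaller group wider | 13.2 to 14.4% | 5.5 to 5.9% |
| 19 vs 65, skewed, ratio 2, larger group wider | 3.5% | 4.8% |

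With a mild difference on the 1–7 day scale (SD 1.5 vs 1.25, 19 vs 65), the rule rejects 6.7% or 3.3%, depending on which group is wider.

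**Reading the table.** Unequal size alone does no harm. Unequal spread alone, with equal arms and symmetric data, does little, and plain ANOVA stays at 5.0 to 5.3% there. The large errors need both together. Skew adds to the inflation when the smaller group is wider, but softens the loss in the other direction (3.5% rather than 1.7%).

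The skewed rows use an unbounded distribution. For a gamma variable with mean 4 and SD 2, the share above 7 is e⁻⁷(1 + 7 + 7²/2 + 7³/6) ≈ 8%. The bounded figure of 12.2% is therefore the closer guide to a 7-day scale.

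**The case against.** The rule is pre-specified and reproducible, and Mann-Whitney is a legitimate test of equal distributions. If the dressing has no effect at all on when ulcers appear, the two distributions coincide and the rule is sound: 5.1% for symmetric days and 4.4% for skewed days, against 5.2% and 5.9% for Welch. At 19 versus 65 the switch even improves on plain ANOVA: with normal data and a 2:1 SD ratio, 10.3% rather than 16.5%. These points stand. They do not rescue the rule, because the section names averages as its target, and twice the nominal level is still wrong for that target.

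The size of the error rests on an assumed SD ratio and direction. That also stands, which is why the mild case is shown beside the 2:1 case.

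A reader might infer three stronger things that the documents do not support.

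- That any difference in size or spread spoils the test. The first two table rows show otherwise.
- That whole-arm comparisons, such as days in the study, are badly wrong. Very high rejection rates with 420 per arm can be produced from unbounded, strongly skewed values, but observation closes at day 7, so such values cannot arise here.
- That the efficacy conclusion is at risk. Neither incidence endpoint nor the sample size depends on this rule.

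**Conclusion.** The point holds in a limited form. The Levene-triggered switch does not correct for unequal variances, separates the test from the reported means and SDs, and does not hold 5% for a comparison of means when unequal spread combines with unequal size or skew.

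For day of onset, an assumed 2:1 SD ratio takes the rule to roughly two to three times nominal in one direction, and below half of nominal in the other for symmetric data. A mild ratio moves it only to about 7% or 3%. All of this is conditional on assumed SDs and shapes, and on the 19 versus 65 split.

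The reach is secondary and descriptive: mainly day of onset, plus any subgroup comparison of a continuous variable. It should be corrected, but nothing in the primary analysis turns on it.

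Welch's test repairs the error rate only. Day of onset compares patients selected by an event after randomisation, so even a correctly sized test of it is not a randomised comparison.

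**What to change.** In the Statistical analysis section, delete the Levene sentence and replace ANOVA with Welch's unequal-variance test for every continuous between-arm comparison, reporting the mean difference with a 95% CI. Name in advance any variable that is better compared by ranks, and report medians for it, so that the choice does not depend on a variance test. Label the day-of-onset comparison descriptive, because it includes only patients who developed an ulcer after randomisation.

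The cost is a few sentences and a negligible loss of efficiency when variances are equal; the level then is unaffected (5.2% at 19 versus 65). Welch is not perfect: at 19 versus 65 with skewed data and a 3:1 SD ratio in the adverse direction it rejects 6.7%, against 24.1% for the protocol's rule. The protocol's section on Ethics Committee approval requires an amendment for changes to the statistical analysis, so the change should be made before outcome data are seen.

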Trial randomizzato e controllato di superiorità in cieco (elaborazione dati) a gruppi paralleli con rapporto di allocazione di 1:1 con randomizzazione a blocchi di 10 e bilanciati per reparto e per area. Non è possibile la cecità degli outcome assesor in quanto nei pazienti del gruppo sperimentale resta spesso una traccia cutanea della presenza della schiuma (impronta cutanea).

Randomized controlled superiority trial (blinded only data processing) with parallel groups.

Allocation ratio of 1: 1 with randomization in blocks of 10 and balanced by department and

by area. The blindness of outcomes assesor is not possible as in the patients of the

experimental group there is often a cutaneous trace of the presence of the foam (skin

impression).

Materials and methods

Areas involved

Surgical Area: general or specialist surgery departments.

Medical Area: geriatrics or neurology or internal medicine departments.

Intensive Area: intensive care or intensive care units.

For each area of each participating center a sample of 40 subjects is expected, randomization

will be done by areas.

Intervention:

Application of MSP in the sacral region within 24 hours of admission and replaced when it

comes off, gets wet or gets dirty in addition to standard preventive care (see below).

MSP is a multilayer foam consisting of: a multi-layered dressing consisting of a polyurethane

foam and a super-absorbent hydrocapillary pad, two layers of polyurethane film, one external

and one internal, and a pressure-sensitive adhesive (PSA) that holds together the two

absorbent layers. The last layer, in contact with the lesion and the skin, is in delicate adhesive

silicone, non-adherent, perforated.

The foam must be raised to the margins at least once a day to check the condition of the

underlying skin. If on the seventh day after randomization the patient is still hospitalized,

after the inspection of the skin, the data collection form (CRF) is closed and the study

concluded.

The medication will be provided free of charge for all the subjects in the studio by the

manufacturer. The company will only supply the dressings. A written agreement was signed

in which the company agrees to provide free samples of the product being studied without

5 di 18

affecting in any way the methodology of drafting the protocol, conducting the study, analyzing the data and publishing the results.

Comparison:

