Standard preventive care. If on the seventh day after randomization the patient is still hospitalized, after the inspection of the skin, the CRF is closed and the study concluded.

Standard preventive care

Evaluation of the risk of developingPD with a Braden scale within 24 hours of admission. Positioning of the patient on a preventive or curative anti-decubitus mattress (static or alternating pressure) if Braden value ≤ 16 or in any case according to the hospital policy, daily inspection of the skin and mobilization of the patient at least every 4 hours (in the surgical patient at least in the post-operative period) if the clinical conditions allow it (NPUAP 2014). Management of incontinence, humidity control and prevention of skin maceration and rubbing / friction during postural changes as per hospital policy.

Method

At the entrance of the patient in the ward, the nurse dedicated to the first reception assesses whether the person has the necessary criteria to be enrolled in the study. In the positive case, he/she will explain to the patient or to his legal guardian, the rationale of the study, he/she will submit the information requesting consent to the participation granting the necessary time for reading and consultation before any consent and signature. If the patient consents, the nurse has the consent signed and attached to the medical record by setting the first part of the CRF (attachment). If the patient at risk refuses the participation, if he/she has other exclusion criteria or if it is not possible to collect the consent, the nurse transcribes it on the CRF and files it. If the patient agrees to participate in the study, the dedicated nurse proceeds to randomization (see below for methods) taking the first opaque envelope according to the external progressive number. It transcribes in the CRF the date, the patient's ID, if he already has PD not to the sacrum and their category and location. It also sign the study arm and other variables of interest. If the patient is in the experimental arm, the nurse, in addition to the standard preventive care, applies the MSP to the sacrum and writes date and time on the CRF and on the MPS. However, the foam must be applied within 24 hours of admission. If this

time interval is exceeded, the researcher will mark the problem in CRF in the "NOTES" part and the patient leaves the study and the CRF is archived.

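### The planned unstratified Fisher test ignores the randomisation strata and is conservative; a stratified Cochran-Mantel-Haenszel test would recover some power at almost no cost

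*Combined protocol and SAP*

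**What the plan says.** **Allocation.** The Design section describes 1:1 allocation "with randomization in blocks of 10 and balanced by department and" by area. Areas involved puts it differently: "For each area of each participating center a sample of 40 subjects is expected, randomization" being done by area. The Randomization section says: "In each ward/area a reference nurse will be identified and 40 envelopes delivered". Sample size also gives 40 patients per participating area of each hospital.

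**Care by site.** Standard preventive care sets common elements for both arms but leaves others to the hospital, for example prevention of "rubbing / friction during postural changes as per hospital policy".

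**Analysis.** Statistical analysis specifies intention to treat, crude incidence, relative risk, relative risk reduction and number needed to treat. For incidence the between-arm test is: "Fisher test will be used to evaluate the differences between the incidences of different outcomes between the experimental group and the control group". Area appears in the subgroup list. Centre and department do not appear in the analysis, and no stratified test or adjusted estimate is planned.

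**The concern.** When allocation is balanced within strata whose risks differ, the natural comparison is made within those strata. A pooled 2x2 table includes between-stratum variation that the design has already removed from the arm difference, so its p-values tend to be too large. Fisher's test is also conservative for a separate reason: with few events only some p-values are attainable. Both effects point the same way, towards missing a real benefit.

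The wording matters as well. A stratified analysis needs one defined stratum, and the protocol describes it in three ways: department and area, area, and ward/area. Take an area with two wards. One series of 40 envelopes does not balance the wards. One series per ward gives 2 x 40 = 80 envelopes against the 40 planned for that area.

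**Working it through.** **1. The plan's own figure.** Inputs from Sample size: "taking into account an alpha error of 0.05 and a beta error of 20" per cent, and "the incidence in the experimental group was 4.5% while in the control group of 15.4" per cent. Two-sidedness is assumed, since it is not stated. With unpooled variances:

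n per arm = (1.960 + 0.842)² x (0.154 x 0.846 + 0.045 x 0.955) / (0.154 - 0.045)² = 7.849 x 0.17326 / 0.011881 = 114.46.

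Twice this is 228.9, which agrees with "it is necessary to enroll at least 228 patients at risk" apart from rounding. The formula is a normal approximation; it does not represent Fisher's test.

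**2. Number of strata.** 840 / 40 = 21 centre-by-area strata, 280 / 40 = 7 per area, 20 per arm in each.

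**3. Fisher's test with no strata at all.** Full enumeration with 420 per arm and one common risk, two-sided at 5%:

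| Common risk | Fisher true size | Chi-square true size |
|---|---|---|
| 5% | 3.5% | 4.9% |
| 6.5% | 3.7% | 5.0% |
| 13.1% | 4.0% | 5.0% |
| 15.4% | 4.0% | 5.0% |

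Strata play no part here, so this shortfall is discreteness alone.

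**4. Separating the two causes.** Simulation of 21 strata of 20 + 20, 10,000 trials per cell. Base control risks are 6.5%, 9% and 13.1%, taken from the Background literature as illustrative values. The between-hospital standard deviation (SD, logit scale) and the relative risk (RR) of 0.6 are assumptions. The tests are:

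- pooled Fisher;
- pooled chi-square, X² = (a - b)² x 2n / [m(2n - m)], with a and b the events per arm, m = a + b and n = 420;
- Cochran-Mantel-Haenszel (CMH), X² = [Σ(a_k - m_k/2)]² / Σ[20 x 20 x m_k(40 - m_k) / (40² x 39)], without continuity correction.

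Each cell gives Fisher / chi-square / CMH, in per cent:

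| SD | Control risks | Type I error | Power, RR 0.6 | Power, RR 0.29 |
|---|---|---|---|---|
| 0 | 6.5-13.1% | 3.5 / 4.6 / 4.7 | 50.3 / 55.6 / 55.6 | 98.4 / 99.0 / 99.0 |
| 0.5 | 3.2-23.9% | 3.4 / 4.7 / 5.0 | 53.8 / 58.7 / 59.4 | 99.0 / 99.3 / 99.3 |
| 1.0 | 1.6-39.5% | 3.1 / 3.9 / 4.9 | 64.0 / 68.3 / 70.7 | 99.8 / 99.9 / 99.9 |

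Simulation standard error is √(0.05 x 0.95 / 10,000) = 0.2 points for type I error and at most √(0.25 / 10,000) = 0.5 points for power.

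At RR 0.6, replacing Fisher by the pooled chi-square gains 5.3, 4.9 and 4.3 points. Stratifying as well adds 0.0, 0.7 and 2.4. The totals are 5.3, 5.6 and 6.7.

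With three area-level strata of 140 per arm, Fisher to CMH goes from 75.4% to 78.5% (all areas at 15.4%), from 69.4% to 73.4% (6.5/15.4/19.2%) and from 82.8% to 87.2% (3/15/35%). The gain over the scenarios shown therefore runs from 3.1 to 6.7 points, typically about 4 to 6.

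**5. The planned effect.** The planned RR is 0.045 / 0.154 = 0.29. At 15.4% against 4.5% with 420 per arm, exact power is 99.97% for Fisher and 99.98% for chi-square. The last column in step 4 shows it is still 98% or more with the lower background risks.

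**6. Within one area.** Sample size asks for the number to be met in each area. At the planned rates, exact Fisher power is 73.9% with 114 per arm (chi-square 81.9%) and 84.1% with 140 per arm (chi-square 88.2%). Fisher reaches 80% at 129 per arm, or 258. This too is discreteness, not stratification.

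**The case against.** The strongest reply is that the plan is safe as written. A conservative test does not produce excess false positives, the balanced design already protects against confounding by area or ward, and at the planned effect the overall comparison has about 99% power. All of this stands. Area is also not absent from the plan: it is a named subgroup factor, and each area is sized separately.

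A reader might infer four stronger things, none of which the documents support.

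- **That ignoring the strata is what makes the test conservative.** Step 3 shows most of the shortfall with no strata, and at SD 0 stratifying gains nothing measurable.
- **That the trial itself expects large risk differences between areas.** The figures of 6.5%, 8.8-9.2% and 13.1% are literature values in the Background. Sample size assumes similar results throughout and the same 280 for every area.
- **That control risk is known to vary by hospital.** Site policy makes this plausible, but Standard preventive care also sets common minimum elements, and no figure for the spread is given.
- **That incomplete blocks leave the pooled estimate unprotected.** One unfinished block of 10 can unbalance a stratum by at most 5 patients, and every stratum simulated here was exactly balanced, so no effect has been shown.

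The mixed wording of the stratum can also be read charitably as centre by area throughout. It is a clarity point, but it has to be settled before a stratified test can be specified.

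**Conclusion.** The concern holds as a matter of efficiency, not validity. The plan's incidence test uses neither centre nor area, and its true type I error with 420 per arm is about 3-4% instead of 5%. The main cause is the discreteness of Fisher's test. Ignoring the strata contributes visibly only with wide between-hospital variation, such as the assumed SD of 1.0.

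The cost is negligible overall at the planned effect and roughly 4 to 6 points of power at an assumed RR of 0.6. A weaker effect is worth allowing for: the planned one comes from a single-centre hip-fracture study, and the protocol itself notes that earlier trial populations were narrow. The area-level shortfall in step 6 applies even at the planned effect if the full losses leave only 114 per arm to analyse.

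These sizes rest on two-sided testing, full strata of 20 + 20, illustrative control risks, and assumed values for the hospital spread and the weaker effect. It would be wrong to conclude that the planned result would be biased or its error rate inflated.

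**What to change.** - **Randomization, Design and Areas involved:** state one stratum in the same words throughout, namely centre by area, with one series of 40 envelopes for each area of each centre. Say that patients who move to another area are analysed in the stratum in which they were randomised.
- **Statistical analysis:** for the primary endpoint and for sacral injury of category II or higher, make the between-arm comparison a Cochran-Mantel-Haenszel test stratified by centre by area, without continuity correction. Report the Mantel-Haenszel relative risk and risk difference with 95% confidence intervals. Keep the pooled Fisher test as a sensitivity analysis.

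Centre and area are known for every patient, so no new data are needed. The cost is a change of wording, made before any outcome data are compared by arm and submitted through the amendment route that the protocol sets out for changes to the statistical analysis. The documents do not show whether the named software version produces this test and these estimates directly, so that should be confirmed when the text is written.
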